#### **Self-Report Outcome Measures (Baseline, Week 4, 8, 20, 32).**

- Heavy Drinking Days (HDD), Drinks per Drinking Day (DDD), and Percent Days Abstinent (PDA) as well as any comorbid drug use (e.g., tobacco use) will be obtained at each assessment using the Timeline Follow Back (TLFB), which is a calendar-based assessment of daily alcohol and drug use (Sobell et al., 1979). The TLFB has been shown to have good psychometric characteristics among a variety of drinker groups and can generate variables that provide a wide range of information about an individual's drinking (e.g., pattern, variability, and magnitude of drinking). HDD is the primary behavioral outcome that will be analyzed. However, secondary outcome measures of interest will also be collected.
- The Impaired Control Scale – Failed Control (ICS-FC) is a 25-item scale that is used to measure the severity of alcohol dependence with respect to dimensions such as impaired control over drinking, awareness of compulsion to drink, etc. (Heather, Booth, & Luce, 1998).
- The Alcohol Dependence Scale (ADS) has been used widely and found to have excellent predictive value with respect to DSM diagnosis (Kivlahan, Sher, & Donovan, 1989).
- The Pennsylvania Alcohol Craving Scale (PACS) is a 5-item measure of craving that will be completed at baseline and at each follow-up session to provide a measure of craving (Flannery, Volpicelli, & Pettinati, 1999). In a recent study, the PACS was found to be a

slightly better predictor of drinking as compared to the OCDS and AUQ (Flannery, Poole, Gallop, & Volpicelli, 2003).

- The Drug Use Questionnaire assesses individual behavior with regard to frequency and quantity of drug use. This measure will be used to assess whether smoking and drug use behavior changes during the course of clinical trial.
- The Beck Depression Inventory-II (BDI-II) consists of 21 scaled statements designed to assess symptoms of depression, with a coefficient alpha of .91 (Beck, Steer, & Carbin, 1988) The BDI-II will be administered at baseline and at last follow-up to examine changes in comorbid depression and covary baseline differences if necessary.
- The Beck Anxiety Inventory (BAI; Beck et al., 1988) consists of 21 items, each describing a common symptom of anxiety. The items are summed to obtain a total score that can range from 0 to 63. The BAI will be administered to examine comorbid anxiety and covary baseline differences if necessary.

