### **Exploratory Aim 1.**

We will also conduct an additional exploratory analysis comparing populations of microbial DNA pre and post-intervention. We will control for age, gender, and diet, because these factors can differentially influence the gut microbiome as well. To do this, we will run a series of OLS multiple

regression models regression microbiome values on age, gender, fruit and vegetable consumption, and the contrast coded intervention (MBRP or RP) group variable both pre and post intervention. A follow-up analysis may include looking within an intervention group, and regressing age, gender, fruit and vegetable consumption and a continuous measure of alcohol use (i.e., total AUDIT score or TLFB drinks per drinking day) on the microbiome values to determine whether there is a dose-response relationship between alcohol intake and changes to the microbiome. We will also explore interactions between changes in the gut microbiome and changes in inflammation and liver function.

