**Questionnaire Measures**  
**Collected at Baseline, 4, 8, 20,**  
**32 weeks**

**Timeline Follow Back (TLFB)**

- The TLFB (Sobell, Maisto, Sobell, & Cooper, 1979) is an assessment method that obtains estimates of daily alcohol, cigarette, and drug use. The TLFB has been shown to have good psychometric characteristics with a variety of drinker groups and can generate variables that provide a wide range of information about an individual's drinking (e.g., pattern, variability, and magnitude of drinking). This instrument requires subjects to recall from memory the number of drinks consumed for each day over the prior 30 days as well as their use of tobacco products and recreational drugs. Studies with alcoholics have shown this instrument to be reliable in assessing drinking frequencies and other behaviors such as arrests and hospitalizations (Sobell et al., 1979).

---

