**Alcohol Use Disorders Identification Test (AUDIT)**

- The AUDIT (Saunders, Aasland, Babor, De La Fuente & Grant, 1993) is used to detect less severe problem drinkers and addresses both current problems (problems within the last 3 months) and problems across an individual’s lifetime. The AUDIT consists of ten questions that cover such domains as alcohol consumption, drinking behavior, adverse psychological reactions, and alcohol-related problems.

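### The optional microbiome dose-response analysis names two poor proxies for alcohol intake, and models microbiome values although its question is about changes

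*Combined protocol and SAP*

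**What the plan says.** In the Data Analysis Plan, Exploratory Aim 1 first compares the arms on microbiome values before and after treatment. It then adds: "A follow-up analysis may include looking within an intervention group". That model involves age, gender, fruit and vegetable intake and "a continuous measure of alcohol use (i.e., total AUDIT score or TLFB drinks per drinking day) on the microbiome values". Its purpose is "to determine whether there is a dose-response relationship between alcohol intake and changes to the microbiome". The two measures follow an i.e., so as written they are the exposure and not examples from a longer list. The text does not say which visit's AUDIT or TLFB is used, over what window, or whether the microbiome value is a change or a single-visit reading.

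The table of instruments under Procedures describes the two sources:

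- **AUDIT.** It has ten questions that "cover such domains as alcohol consumption, drinking behavior, adverse psychological reactions, and alcohol-related problems". It "addresses both current problems (problems within the last 3 months) and problems across" the person's lifetime.
- **TLFB.** Participants "recall from memory the number of drinks consumed for each day over the prior 30 days". It appears under the heading "Self-Report Outcome Measures (Baseline, Week 4, 8, 20, 32", so it is taken at baseline and at weeks 4 and 8 among other visits.

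The section on gut microbiome sampling places stool collection at baseline and week 8.

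**The concern.** A dose-response analysis needs an exposure that rises and falls with the amount drunk. Drinks per drinking day is intensity on the days when drinking happens, and frequency is left out. The AUDIT total is a severity score in which consumption is only one domain. Neither has to track total intake, and they can fail in different ways. The outcome has a parallel mismatch: the question is about change, but the model is written for values. A single-visit regression cannot separate change from stable differences between people.

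At stake is the interpretation of this one analysis. A real relationship could be weakened or missed. An AUDIT association could reflect long-standing severity and not recent drinking. Participants who stop drinking, and so have the largest fall in intake, may have no usable value of drinks per drinking day.

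**Working it through.** The plan gives no sample size, power or effect size for Exploratory Aim 1, so there is no figure to reproduce. The checks below use the definitions in the documents, with assumptions marked.

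**1. Drinks per drinking day (DDD) against total drinks.** Total drinks = DDD × number of drinking days. Over a 30-day TLFB:

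| DDD | Drinking days | Total drinks |
|---|---|---|
| 6 | 1 | 6 |
| 6 | 15 | 90 |
| 6 | 30 | 180 |
| 12 | 2 | 24 |
| 3 | 30 | 90 |

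The same score of 6 covers a 30-fold range of intake (180/6). Rankings can also reverse: a score of 12 goes with 24 drinks and a score of 3 with 90.

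**2. Abstainers.** With no drinking days, DDD = 0/0. The inclusion criteria require a last drink within 10 days, so DDD should be defined in the baseline 30-day window. The gap arises on treatment, where the section on MBRP and RP implementation encourages abstinence without requiring it. The documents do not say how many participants to expect with no drinking days.

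**3. AUDIT window at week 8.** Taking 3 months as 91 days and treatment as 8 × 7 = 56 days, 91 − 56 = 35 days fall before treatment, and 35/91 = 38% (38–39% for 90 to 92 days). This is a share of days in the recall window, not a share of the score. The lifetime content comes on top; the documents do not say how many items it covers.

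**4. What the TLFB can supply.** Assume the visits fall on treatment days 28 and 56.

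- The week-8 TLFB covers days 27 to 56: 30 of 56 treatment days (54%).
- The week-4 TLFB covers days −1 to 28: 28 treatment days.
- Days 27 and 28 are in both, so together they cover 28 + 30 − 2 = 56 of 56 days (100%).

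**5. How weak a proxy DDD might be.** The documents give no variability figures, so this is an illustration only. Assume DDD centred near 6, about 12 drinking days per 30 (held between 1 and 30), coefficient of variation 0.3–0.5 for DDD and 0.3–0.8 for frequency, and a log-scale correlation between them of −0.3 to 0.6. The simulated correlation of DDD with total drinks then runs from 0.20 to 0.92.

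**6. What dilution could cost.** Take a true correlation of 0.30 between intake and the microbiome measure and a proxy correlation of 0.6, with DDD related to the microbiome only through intake. The observable correlation is 0.30 × 0.6 = 0.18. Approximate two-sided 5% power is Φ(atanh(r)·√(n − 3) − 1.96), ignoring covariates. The data-sharing section plans about 150 metagenomes. With equal arms that is about 75 per arm if it means participants, or about 37 if it means two samples each.

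| n per arm | Power at r = 0.30 | Power at r = 0.18 |
|---|---|---|
| 75 | 0.75 | 0.34 |
| 37 | 0.44 | 0.18 |

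**The case against.** The strongest defence is that this is an optional add-on to an exploratory aim. Hypothesis 5 concerns differences between MBRP and RP, not alcohol dose. That stands, and it sets the low priority of the point.

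A second defence is that the 8-week exposure window is inferred from the stool sampling times; the analysis text names none. Changes to the microbiome could also mean alteration associated with chronic heavy drinking, which is how the background on alcohol and the gut microbiome is framed. On that reading a baseline severity score has some logic, and a baseline AUDIT contains no treatment days to mix. This stands in part. It does not make either measure one of intake, which is the word the plan uses, and the unstated visit and window are themselves a gap.

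A reader might go further and infer that the analysis cannot show a dose-response at all. The documents do not support that: DDD is one factor of total intake and will usually carry some of its signal, and the AUDIT includes a consumption domain. Nor is the 30-day TLFB window a defect of DDD, since DDD and total drinks come from the same daily records. It would also be wrong to argue that treatment lowers intake mainly by cutting drinking frequency. The documents do not say so, and the goal-setting session allows for both reduction and abstinence. Finally, 1 versus 30 drinking days is an arithmetic extreme in a sample recruited for consistent heavy drinking. It shows what the measure ignores, not a typical error.

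**Conclusion.** The point holds as a mismatch between question and variables. DDD ignores frequency and is undefined without drinking days. The AUDIT total is a mixed severity score with long recall. The outcome is written as values where the question is about changes. The likely result is dilution or distortion of a true dose-response, with possible loss of abstainers from the model.

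The size of the dilution cannot be fixed from the documents. The proxy correlation of 0.20 to 0.92 and the power figures rest on assumed variability and an assumed effect. The 56-day TLFB coverage rests on visits at days 28 and 56. No primary or secondary conclusion is affected. This is a free improvement to an exploratory analysis.

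**What to change.** In Exploratory Aim 1 of the Data Analysis Plan:

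- **Exposure.** Replace both named measures with TLFB total drinks, or mean drinks per day over all days with abstinent days counted as 0. Use the baseline 30-day TLFB for pre-treatment intake, and the week-4 and week-8 TLFBs together for the 56 treatment days, counting each calendar day once. A gap opens if the two visits are more than 30 days apart, so state how uncovered days are handled.
- **Scale.** If change in intake is used, take it per day (treatment total/56 minus baseline total/30), because the windows differ in length. A constant 2 drinks a day gives 60 drinks over 30 days but 112 over 56.
- **Outcome.** Relate intake, or its per-day change, to the baseline-to-week-8 microbiome change, for example the week-8 value adjusted for the baseline value. Keep age, gender and fruit and vegetable intake as covariates.
- **AUDIT.** Keep it as a baseline descriptor of severity.

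The cost is a change of wording and a short derivation. All the data are already planned.

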### **Differential attrition analyses.**

Attrition analyses will be conducted after each follow-up data collection effort to provide assurance that differential attrition by treatment condition has not occurred. Following previously published procedures (Jurs & Glass, 1971), a series of ANOVAs of treatment (MBRP versus RP) X retention (retained, not retained) will be conducted on continuous baseline measures. Significant treatment X retention interactions identify measured variables on which differential attrition may have occurred. The logit model analog procedure will be applied to categorical baseline measures to test for differential attrition on categorical variables such as gender and ethnicity (Agresti, 1990). We will conduct these analyses to assure that differential attrition by treatment condition does not account for any of the effects of the treatments.

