#### **The impact of attrition.**

It is anticipated that some attrition will occur in this population, though we do not anticipate differential attrition by condition. A conservative estimate of 20% attrition over the course of data collection is assumed. Recently published evidence suggests an attrition rate of approximately 20% for other trials. In our own previous trials, we have seen attrition of around 20%. Thus, sample size will need to be increased by 20% over minimum requirements. After final attrition has been calculated, pretest differences on alcohol use and problems will be compared among individuals who finished the study versus those who did not and by condition, to determine whether these two groups differed in

systematic ways and whether these differences were related to treatment condition.

With respect to attrition during the follow-up period, all participants will update their address and phone number as well as the name and number of an individual who always knows how to reach them at every visit. The project coordinator will also contact each patient in between follow-up visits.

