#### ***Data Analysis Plan:***

Analyses will be conducted using SAS Version 9.3 and EQS for Windows Version 5.7b. We will conduct extensive analyses of any attrition encountered in the project to determine bias. However, note that in each of the analyses described herein, we will have the capability of using modern approaches to the handling of missing data (Schafer & Graham, 2002) including full information maximum likelihood (FIML) estimation of missing data within Proc Mixed in SAS and within EQS.

Descriptive analyses. The distributional properties of all continuously scaled variables will be examined for skewness and kurtosis to determine the need for normalizing transformations or for alternations to our analysis plan (i.e., generalized estimating equations in SAS or robust estimation in EQS) prior to the primary analyses.

Pretest equivalence. To confirm the validity of random assignment, pretest equivalence of the two treatment conditions across demographics, drinking history, smoking, and all other baseline measures will be assessed via t-tests on continuous items and  $\chi^2$  tests of categorical items. We will use the Bonferroni approach (Keppel, 1991) to correct for alpha inflation with a familywise alpha of .05. Any variables on which the two groups are unequal at pretest will be covariates in all further analyses.

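### The specified attrition tests compare baseline profiles, not drop-out by arm, so they cannot give the assurance about differential attrition that the plan asks of them

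*Combined protocol and SAP*

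**What the plan says.** The section on differential attrition analyses (Data Analysis Plan) gives the purpose: "Attrition analyses will be conducted after each follow-up data collection effort to provide assurance that differential attrition by treatment condition has not occurred". For continuous variables, "a series of ANOVAs of treatment (MBRP versus RP) X retention (retained, not retained) will be conducted on continuous baseline measures". For categorical variables, "The logit model analog procedure will be applied to categorical baseline measures to test for differential attrition on categorical variables such as gender and ethnicity". The reading of a positive result is that "Significant treatment X retention interactions identify measured variables on which differential attrition may have occurred". The section closes by saying that the analyses are done to assure that differential attrition does not explain any treatment effect.

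Two other places bear on this. Under the impact of attrition (Power Analysis), the plan assumes 20% loss, says "we do not anticipate differential attrition by condition", and adds that "pretest differences on alcohol use and problems will be compared among individuals who finished the study versus those who did not and by condition". The opening of the Data Analysis Plan says "We will conduct extensive analyses of any attrition encountered in the project to determine bias" and names no test.

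**The concern.** Differential attrition by condition most directly means that one arm loses more people than the other. Neither of the two passages that describe a comparison sets the proportion lost in MBRP against the proportion lost in RP. Both work on baseline measures.

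Drinking after baseline is also left out, although the protocol ties it to loss. Under the in-person procedures (Baseline Session), participants are breath-tested before each session. A positive test, repeated at the rescheduled visit the next day, counts as a missed session, and more than one missed session leads to removal from the study. If Hypothesis 1 is right and drinking falls more under MBRP, this route could remove more RP participants. That is an inference from the protocol's own rules, not a prediction that it makes.

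What is at stake is the attrition statement in the trial report. A set of nonsignificant interactions could be offered as grounds for discounting differential attrition when the tests could not have seen a difference in rates.

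**Working it through.** **Inputs.** From the plan: 113 per arm (Specific Aim 1); 20% attrition (impact of attrition); two-sided alpha .05 (Sample Size Requirements); correlation .50 between assessments and smallest prior effect d = .23 (Power for Specific Aim 1). Assumed by me: the 30%/10% split, the dependence of loss on baseline, and leavers .5 SD worse than stayers.

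**1. The plan's own figures.** 180/(1 − .20) = 225. Per arm, 90/.80 = 112.5, rounded up to 113, or 226 in all. The recruitment target reproduces. The plan gives no operating figure for the attrition check.

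**2. What the interaction estimates.** It is (leavers' baseline mean − stayers' baseline mean) in MBRP minus the same quantity in RP. The drop-out proportions affect its precision through the cell sizes, but they are not what it tests.

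**3. Rejection rates.** 10,000 simulated trials per row, 113 per arm, one standard normal baseline measure:

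| Loss by arm | Dependence on baseline | Interaction test | Direct comparison of rates |
|---|---|---|---|
| 20% v 20% | none | 5.3% | 5.2% |
| 30% v 10% | none | 5.0% | 97.2% |
| 30% v 10% | log-odds slope .5 per SD, both arms | 5.3% | 97.3% |
| 30% v 10% | slope .7 in the high-loss arm only | 41% | 97.2% |

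Formula check of the direct comparison: [.20 − 1.96 × √(2 × .20 × .80/113)] / √((.30 × .70 + .10 × .90)/113) = (.200 − .104)/.0515 = 1.86, which gives power .968.

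The interaction reacts only when the dependence on baseline differs by arm. A 30%/10% split averages 20%, so the overall attrition figure would not reveal it.

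Observed losses of 34/113 and 11/113 would give a difference of 20.4 points (95% CI 10.3 to 30.4). Power of the direct test falls to 86% for 28% v 12% and to 47% for 25% v 15%, so the interval is needed as well as the p-value.

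**4. Precision on the interaction's own question.** In SD units, SE = √(2 × (1/kept + 1/lost)), with counts per arm, and 80% power needs 2.80 × SE.
- 20% loss (90.4 kept, 22.6 lost): SE = .333, detectable gap .93 SD.
- 10% loss (101.7 kept, 11.3 lost): SE = .443, detectable gap 1.24 SD.

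**5. Does this reach the HDD estimate?** With 30% v 10% loss and leavers .5 SD worse, the observed-case arm difference shifts by (.30 − .10) × .5 = .10 SD. The plan uses FIML, not observed cases. At a common correlation of .50, three earlier visits (baseline, weeks 4 and 8) predict a share 3 × .25/(1 + 2 × .50) = .375 of the variance of a later HDD value.
- Loss depends on arm alone: no bias.
- Loss follows recorded HDD: about 0 after FIML.
- Loss follows the unseen HDD: about (1 − .375) × .10 = .06 SD remains. If only baseline HDD is available, as for someone removed before week 4, about (1 − .25) × .10 = .075 SD.

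**The case against.** The strongest case is that this is a diagnostic that does not enter the primary analysis, and that the plan is less closed than it looks. Much of that stands, and it rules out several stronger readings.

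- **That the HDD result is biased by .10 SD.** A reader might take the observed-case figure this way. It does not apply to the planned estimator, and loss that depends on arm alone causes no bias at all.
- **That a null result will be declared an exclusion.** The section defines only what a significant interaction means. Its assurance wording states a purpose, and no decision rule turns a null into a finding of no differential attrition.
- **That rates will never be compared.** The Data Analysis Plan's general promise on attrition leaves room for it. The cited published procedure is not available here, the logit analogue could contain a treatment by retention term (though no test of it is named), and the counts by arm are the cell sizes of every planned ANOVA. A comparison is unspecified rather than ruled out.
- **That MBRP is more burdensome and so will lose more people.** The section on MBRP and RP implementation gives RP the same format, time, location and amount of homework. Only the content differs.
- **That the check would come back clean.** No multiplicity correction is stated, and with 20 independent baseline tests the chance of at least one significant interaction is 64%. That chance is the same with or without a gap in drop-out, so it says nothing about rates.

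The baseline interactions are also a valid check on whether the profile of leavers differs by arm. They are incomplete, not wrong. What the objection does not answer is the mismatch between the stated purpose and the tests specified to serve it.

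**Conclusion.** The concern holds as a mismatch between method and stated conclusion. The specified tests cannot separate 30% v 10% loss from equal loss when drop-out is unrelated to baseline or depends on it equally in both arms (about 5% rejection either way, against about 97% for a direct comparison). They do not use post-baseline drinking. Even for the baseline profile they are reliable only for gaps near 1 SD.

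The 30%/10% split and the slopes are illustrations, and the documents do not predict unequal loss. The primary HDD estimate is not shown to be biased. A residue of about .06 SD, set beside the plan's d = .23, arises only if loss follows unseen HDD with leavers .5 SD worse and correlation .50. The point is worth correcting because the trial's attrition statement will rest on this section.

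**What to change.** In the section on differential attrition analyses:

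1. Report retention (n/N) and reasons for loss by arm at weeks 4, 8, 20 and 32, with the arm difference in retention and its 95% CI.
2. Add a logistic model of loss at the next visit on arm, most recent observed HDD and their interaction.
3. Keep the baseline treatment by retention interactions as description, reported with confidence intervals.
4. Replace the two statements that use assurance and assure. Say instead that these analyses describe attrition and that a nonsignificant result does not exclude differential attrition.

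The cost is a change of SAP wording and a few lines of code on data the trial already collects. The downside is a less reassuring statement about attrition in the report.
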